3.10. Analysis of the primary outcome

3.10.1. Main analysis

The difference between the two treatment arms in QoL after 3 months, as assessed with KCCQ-OSS, will be tested with the use of an ANCOVA analysis, using baseline QoL as a covariate. The difference will be presented as the average treatment effect for liberal fluid – restricted fluid arm. The estimated difference will be presented with a point estimate and 95% confidence interval. A p-value of <0.05 will be considered significant.

For the primary analysis, the intention-to-treat principle will be applied.

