3.10.3. Subgroup analyses

The following prespecified subgroups will be analysed in relation to the primary endpoint: Sex at birth (male/female), including centre, HF type based on last known EF (HFrEF ≤40%/HFmrEF 41-49%/HFpEF ≥50%), NYHA class (II/III), age (above/below median), BMI (above/below median), baseline diuretic dosage (above/below median), DM (yes/no), and baseline sodium, urea, creatinine, and NT-proBNP concentrations (above/below median).

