- 2. To investigate the effect of increased fluid intake in the subgroup of patients who were prescribed a fluid restriction at baseline on the primary, (key) secondary and explorative endpoints

Analysis:

- 1. Population: Patients who were prescribed any form of fluid restriction prior to randomisation will be included.
- 2. Population: Patients who were prescribed any form of fluid restriction prior to randomisation and who were randomised to liberal fluid intake. Patients will be divided into two groups for analysis based on their average fluid intake at week 6 (less or more than 2L).
- 3. Population: Patients who were prescribed any form of fluid restriction prior to randomisation. Patients will be divided into three groups:
 - a. Randomised to fluid restriction.
 - b. Randomised to liberal fluid intake and a fluid intake of less than 2L based on their average fluid intake at week 6.
 - c. Randomised to liberal fluid intake and a fluid intake of more than 2L based on their average fluid intake at week 6.

The analysis on the primary, (key) secondary and exploratory endpoints will be performed as described in '3.10 Analysis of the primary outcome', '3.11. Analysis of the secondary outcomes' and '3.12 Analysis of other outcomes'.

Thirst and QoL analysis

Aim:

- 1. To investigate the relationship between thirst and QoL.
- 2. To investigate the effect of thirst status on the effect of liberal fluid intake versus fluid restriction.

Analyses:

- 1. Population: All patients with completed KCCQ and TDS-HF
 - a. At baseline;
 - Correlation between baseline KCCQ-OSS (and subdomains) and TDS-HF
 - A multiple regression analysis between baseline KCCQ-OSS (and subdomains) and TDS-HF.
 - b. Follow-up;
 - Correlation between the change in KCCQ-OSS and subdomains and TDS-HF per randomisation arm.
- 2. Population: Patients will be categorized into based on the TDS-HF:
 - a. No thirst (score = 8).
 - b. Minimal to moderate thirsty (score = 9 to 24).
 - c. Moderate to very thirsty (score = 25 to 40).

The analysis on the primary and secondary endpoints will be performed as described in '3.10 Analysis of the primary outcome' and '3.11. Analysis of the secondary outcomes'. Baseline characteristics will include all subdomains of the KCCQ.

In depth analysis

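### The thirst sub-analysis asks whether thirst status changes the treatment effect, but the SAP plans no interaction test and does not say which visit's TDS-HF score defines the thirst groups

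*SAP*

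**What the plan says.** SAP section 4, under the thirst and QoL analysis, gives as its second aim "To investigate the effect of thirst status on the effect of liberal fluid intake versus fluid restriction". Patients are put into three groups by TDS-HF: a score of 8 (the floor of the scale), 9 to 24, and 25 to 40. The visit at which that score is taken is not named. The method is then given by reference: "The analysis on the primary and secondary endpoints will be performed as described in" sections 3.10 and 3.11.

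Section 3.10.1 says that the arm difference in 3-month KCCQ-OSS "will be tested with the use of an ANCOVA analysis, using baseline QoL as a covariate", reported with a point estimate, a 95% confidence interval and a p-value judged at 0.05. Section 3.11 uses a similar approach for the secondary questionnaires.

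Section 3.10.3 says "The following prespecified subgroups will be analysed in relation to the primary endpoint" and lists them. Thirst is not on the list, and no interaction test is mentioned. The paragraph on in-depth analysis at the end of section 4 calls for further exploration when subgroup results give a signal of effect modification, but sets no criterion for a signal.

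**The concern.** The null hypothesis of aim 2 is that the effect of liberal versus restricted intake is the same whatever the thirst status. The null hypothesis of the ANCOVA in 3.10.1 is that there is no difference between the arms. Applying the second within each thirst group gives three answers to a different question, and no planned quantity compares them.

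With no comparison specified, a reader of the results may fall back on asking which groups reach p<0.05. Groups that share one true effect often differ in significance by chance and by size. Because the analysis is prespecified, a spurious pattern would carry that label in a report on which patients benefit.

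The missing visit adds to this. TDS-HF at 3 months is the key secondary outcome, so groups formed on it would condition on a result of treatment. Reporting baseline characteristics by group hints at baseline scores, but the fluid-management analysis in the same section groups patients by intake at week 6. The visit cannot be taken for granted.

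**Working it through.** **Inputs from the SAP (2.5, 2.6, 3.10.1).** Difference 2.5 points, SD 20, baseline to follow-up correlation 0.88, alpha 0.05, power 80%, 454 evaluable, 1:1 allocation, TDS-HF mean 16 and SD 8. Two-sided testing is assumed from the 95% interval.

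**The plan's own figure.** Residual SD = 20 × √(1 − 0.88²) = 9.50. Per arm, n = 2 × (1.960 + 0.842)² × 9.50² / 2.5² ≈ 226.7, so 227, or 454 in total. This matches the SAP.

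**Group shares (assumed; the SAP gives none).**
- A normal curve with mean 16 and SD 8, with scores up to 8 put in the first group, gives 17.4/68.2/14.4%, or n = 79/310/65.
- Eight plus an exponential with mean 8 gives 6.1/81.2/12.7%, or n = 28/369/58.
- Equal thirds serve as a reference.

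**Power within a group, uniform effect of 2.5.** SE = 2 × 9.50/√n. For the first split:
- n = 79: SE 2.14, power 21.5%
- n = 310: SE 1.08, power 64.0%
- n = 65: SE 2.36, power 18.6%

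**Mixed pattern (some groups significant, some not).** This is 1 − P(all) − P(none):
- P(all) = 0.215 × 0.640 × 0.186 = 0.026
- P(none) = 0.785 × 0.360 × 0.814 = 0.230
- Mixed = 1 − 0.026 − 0.230 = 0.744

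The same calculation for other cases, with no effect modification in any row:

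| True uniform effect | Correlation | Shares | Mixed pattern |
|---|---|---|---|
| 2.5 | 0.88 | 17/68/14 | 74% |
| 2.5 | 0.88 | 6/81/13 | 78% |
| 2.5 | 0.88 | equal thirds | 70% |
| 0 | 0.88 | 17/68/14 | 14% |
| 1.25 | 0.88 | 17/68/14 | 34% |
| 3.75 | 0.88 | 17/68/14 | 84% |
| 5 | 0.88 | 17/68/14 | 63% |
| 2.5 | 0.8 | 17/68/14 | 59% |
| 2.5 | 0.7 | 17/68/14 | 48% |
| 2.5 | 0.6 | 17/68/14 | 42% |

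The no-effect row can be checked directly: 1 − 0.95³ − 0.05³ = 0.1425. An extreme 5/90/5 split at 2.5 points gives 80%.

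**Interaction test.** Its null hypothesis is true in every row, so it should reject in 5%. Simulation of a 2-df arm-by-group F test (8,000 trials per scenario, effects of 0 and 2.5, three splits) gave 4.7 to 5.2%.

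**Precision of the right quantity.** For the 17/68/14 split, the SE of the difference in effect between the outer groups is √(2.14² + 2.36²) ≈ 3.2 points. A difference of about 2.80 × 3.2 ≈ 9 points would be needed for 80% power.

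**The case against.** The SAP does not say that the ANCOVA is run separately in each group, nor that aim 2 is settled by which groups reach p<0.05. It asks for point estimates and 95% intervals, which a careful reader could compare, and it treats a signal only as a prompt for exploration. This stands: the defect is a missing comparison, not a stated wrong decision rule.

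Four stronger readings are tempting, and the documents do not support them.
- *The analysis will usually suggest modification when there is none.* That needs a true effect near 2.5 points, a correlation near 0.88, and mixed significance being read as modification. With no effect, half the effect, or a correlation of 0.7, it is not usual.
- *Unequal groups are the cause.* Equal thirds still give 70%. Size mainly decides which group is significant.
- *The likely result is that only the middle group appears to benefit.* At the design values, this pattern occurs in 41% of trials under the first assumed split and 53% under the second.
- *Thirst is the proposed mechanism.* The rebuttal letter in the Protocol document says that the thirst scale covers one aspect of the study, and names daily monitoring as one of the main burdens of restriction.

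The group shares are also uncertain. The mean of 16 and SD of 8 are a power input for thirst at 3 months, not a baseline distribution, and a normal curve puts about 16% of patients below the scale's floor. This stands as a caveat, but the result varies little with the shares. Finally, the interaction estimate will rarely be decisive. That is true, but an imprecise estimate of the right quantity is better than none.

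**Conclusion.** The point holds as a mismatch between aim and analysis. Aim 2 asks about effect modification, and nothing in 3.10, 3.10.3, 3.11 or section 4 estimates or tests it. The score that forms the groups is not tied to a visit.

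The figure of 70 to 78% applies only if within-group p-values are compared, and only for a uniform effect at the plan's design values with assumed group shares. It shows what the gap allows, and does not predict what the investigators will conclude. The consequence is confined to one aim of a sub-analysis. The change should be made because it is cheap and the aim otherwise goes unanswered.

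**What to change.** In SAP section 4, for aim 2:

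1. State that the thirst groups use the baseline (pre-randomisation) TDS-HF score.
2. Fit one ANCOVA in all randomised patients: 3-month KCCQ-OSS on arm, baseline KCCQ-OSS, baseline TDS-HF (continuous, or the three prespecified categories; choose one in advance) and the arm-by-TDS-HF interaction.
3. Report the interaction estimate with its 95% CI as the exploratory answer to aim 2. Show the group effects with 95% CIs for description only.
4. Use the same form for the secondary questionnaires. Where TDS-HF is itself the outcome, a single model also avoids a practical problem: everyone in the first group has a baseline score of 8, so the covariate is constant in that group and scores cannot improve.
5. Say what counts as a signal in the in-depth paragraph. Since 3.10.3 has the same gap, one sentence there on interaction estimates could serve both places.

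The cost is a few lines of text, and the data are already collected. The downside is imprecision (an SE of about 3.2 points between the outer groups under the 17/68/14 split). The plan should say so, and should say that a non-significant interaction is not evidence of a uniform effect.

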2.3. Outcomes

2.3.1. Primary outcome

• QoL as assessed by KCCQ-OSS¹ at 3 months after randomisation

2.3.2.Secondary outcome

Key secondary outcome:

• Thirst distress as assessed by the TDS-HF¹

Other secondary outcomes:

- QoL at 3 months as assessed by KCCQ-CSS
- QoL at 3 months as assessed by each of the KCCQ domains and the proportion of patients with clinically meaningful changes in these scores
- QoL at 3 months as assessed by EQ-5D-5L¹
- Patient-reported fluid intake in week 6
- Safety: The composite clinical endpoint: death, all-cause hospitalisation and the requirement of iv-loop diuretics during the 6-month clinical follow-up duration

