3.11. Analysis of the secondary outcomes

For the secondary parameters thirst distress, as assessed with the TDS-HF, and QoL at 3 months after randomisation, as assessed with the KCCQ-CSS, each of the KCCQ domains and the EQ-5D-5L, a similar approach as for the primary study parameters will be adopted.

The difference between groups in proportion of patients with clinically meaningful changes (defined as a difference of 5 points compared to baseline) in KCCQ-OSS and KCCQ-CSS (8, 10) and the percentage of events (death, all-cause hospitalisations, the need for iv-loop diuretics and acute kidney injury) will be tested with Chi-square or Fisher exact test, whichever appropriate. The

difference in between groups patient reported fluid intake will be analysed with a Students' t test or Mann-Whitney U test, whichever appropriate.

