Appendix 2: Scoring of the questionnaires

1. Kansas City Cardiomyopathy Questionnaire (KCCQ)

The KCCQ is scored according to 'The Kansas City Cardiomyopathy Questionnaire Scoring Instructions'. In brief, each answer option is assigned an ordinal value starting with 1 (indicating the lowest level of performance). Within each domain, all scores are summed up and converted to a 0 to 100 scale by subtracting the lowest possible scale score, dividing by the range of the scale and multiplying by 100. As described in the scoring instructions, at least one or two questions, depending on the domain, need to be answered before any score can be assigned. Missing values of each domain will be assigned the average of the answered items within that same domain (17).

The Overall Summary Score is calculated as the mean of the following available summary scores: Physical Limitation Score, Total Symptom Score, Quality of Life Score and Social Limitation Score.

The handling of missing KCCQ questionnaires is described in '3.10.4. Treatment of missing data'.

2. Thirst Distress Scale for Heart Failure

The eight items, on thirst dimensions, are rated on a 5-point Likert scale from 1 (strongly disagree) to 5 (strongly agree). The total score ranges from 8 (no thirst) till 40 (very thirsty) (18).

In case of at least two missing items on the questionnaire, the questionnaire is excluded from the analyses. If only one item is missing, this item will be scored as the mean of the other items on the questionnaire.

3. European Quality of Life Five Dimensions Five Levels guestionnaire (EQ-5D-5L)

The EQ-5D-5L consist of two parts. The first part assess five domains of health (mobility, self-care, usual activities, pain and discomfort, anxiety and depression) which all has five levels of response (no problems, slight problems, moderate problems, severe problems, extreme problems/unable to). This generates a health state which can be summarised in an index score generally range from less than 0 (where 0 is the value of a health state equivalent to dead; negative values representing values as worse than dead) to 1 (the value of full health), with higher scores indicating higher health utility. The health state is region specific (19). The second part consists of a visual analogue scale raging form 0 (worst imaginable health) to 100 (best imaginable heath).

In case of at least one missing item the questionnaire will be excluded from the analyses (20).

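### Two sub-analyses in SAP section 4 analyse an outcome in groups formed on that same variable (week-6 fluid intake, and TDS-HF with its scale minimum)

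*SAP*

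**What the plan says.** **Fluid management.** In SAP section 4 (Change of fluid management analysis), analysis 2 takes liberal-arm patients with a prior fluid restriction and states: "Patients will be divided into two groups for analysis based on their average fluid intake at week 6 (less or more than 2L". Analysis 3 uses the same split and adds the restriction arm as a third group. The primary, secondary and exploratory endpoints are then analysed as in sections 3.10 to 3.12. Section 2.3.2 lists "Patient-reported fluid intake in week 6" as a secondary outcome, and section 3.11 assigns it a t test or Mann-Whitney test between groups.

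**Thirst.** The second aim of the Thirst and QoL analysis is: "To investigate the effect of thirst status on the effect of liberal fluid intake versus fluid restriction". The grouping instruction reads "Population: Patients will be categorized into based on the TDS-HF", with no time point. The groups are 8, 9 to 24 and 25 to 40, the lowest being labelled "No thirst (score = 8". The endpoints follow: "The analysis on the primary and secondary endpoints will be performed as described in" sections 3.10 and 3.11. The key secondary outcome is TDS-HF, for which section 3.11 says "a similar approach as for the primary study parameters will be adopted", that is, the baseline-adjusted ANCOVA of section 3.10.1. Appendix 2 gives the scale: "The total score ranges from 8 (no thirst) till 40 (very thirsty". The lowest group is therefore at the scale minimum.

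Section 4 neither removes the grouping variable from the endpoints nor mentions the scale minimum.

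**The concern.** When a variable both forms the groups and serves as the outcome, the result partly reflects how the groups were made.

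For week-6 intake the problem is complete. Everyone in one group drinks more than everyone in the other, so the p-value carries no information.

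For TDS-HF the problem is partial. With baseline grouping, each patient in the lowest group starts at 8 and cannot score lower. Liberal intake can show a benefit there only by preventing a rise. An effect of the same underlying size in everyone would then look graded by thirst group. At stake is a published statement that liberal intake relieves thirst only in patients who are already thirsty, when the scale limit could explain part or all of that pattern. If the groups were instead formed on month-3 TDS-HF, the outcome itself would define them and the within-group comparison of arms would no longer be randomised.

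**Working it through.** **1. The plan's own TDS-HF figure.** Inputs from SAP section 2.6: difference 1.5, SD 8, correlation 0.88, 80% power, alpha 0.05 (taken as two-sided).
- Adjusted SD = 8 × √(1 − 0.88²) = 3.80.
- n per arm = 2 × (1.96 + 0.84)² × 3.80² / 1.5² ≈ 101, so 202 in total.
- With 454 evaluable patients, power is about 98.8%. The plan's claim of adequate power for TDS-HF holds overall. No figure is given for the sub-analyses.

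**2. Week-6 intake split at 2 L.** The documents give no intake distribution. Assumed: normal, mean 1900 ml, SD 400 ml, 200 patients.
- Standardised cut = (2000 − 1900)/400 = 0.25; normal density there 0.3867; share above 0.4013.
- Mean above = 1900 + 400 × 0.3867/0.4013 = 2285 ml. Mean below = 1900 − 400 × 0.3867/0.5987 = 1642 ml. Difference about 644 ml.
- Within-group SD = √(400² − 0.4013 × 0.5987 × 644²) ≈ 246 ml. SE = 246 × √(1/80.3 + 1/119.7) ≈ 35.5. t ≈ 18, p of the order of 10⁻⁴⁴.
- Single simulated samples of 200 gave about 620 and 660 ml, with p about 10⁻⁴⁴ and 10⁻⁴³.

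The Mann-Whitney option needs no distributional assumption. Separation is complete, so z = √(3 × n₁ × n₂/(N + 1)). With 80 and 120 patients, z = √(3 × 9600/201) ≈ 12.0; with 20 and 180 it is √(3 × 3600/201) ≈ 7.3. In analysis 3 this applies to the contrast of the two liberal-arm groups.

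**3. TDS-HF by baseline thirst group.** Assumed: a latent normal score, rounded and limited to 8 to 40, with the same latent effect in every patient. A latent mean of 14.27 and SD of 10.51 reproduce the plan's observed mean 16 and SD 8. About 29% of patients then score 8, 54% score 9 to 24 and 16% score 25 to 40. An observed overall difference of 1.5 requires a latent effect of about 2.2.

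| Observed correlation | Score 8 | 9 to 24 | 25 to 40 | Interaction test rejects (N = 454) |
|---|---|---|---|---|
| 0.88 (plan) | -0.4 | -1.9 | -2.1 | about 42% |
| 0.72 (assumed) | -0.7 | -1.8 | -2.1 | about 16% |

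- Check at 0.88: 0.29 × 0.4 + 0.54 × 1.9 + 0.16 × 2.1 ≈ 1.5.
- The lowest group shows 0.4/2.2 ≈ 18% to 0.7/2.2 ≈ 32% of the latent effect; the top group shows 2.1/2.2 ≈ 95%.
- With no treatment effect the interaction test rejects in about 5% of trials.
- Rejection rates vary by a few percentage points between simulation runs.

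**4. Range under other assumptions.** With a latent effect of only 1.5 (observed overall about 1.0 to 1.2), latent correlations of 0.60 to 0.88, and the latent score either calibrated as above or set directly to mean 16 and SD 8, the score-8 effect is -0.33 to -0.80 and rejection is 6% to 17%.

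**The case against.** A reader might infer that the floor by itself produces a false signal of effect modification. The documents do not support that, for three reasons.
- A floor only shrinks an effect that exists. With no treatment effect the rejection rate stays near 5%.
- The SAP names no interaction test for this sub-analysis. Sections 3.10 and 3.11 give a comparison between arms, so the rejection rates above describe a test that a reader might add. The clause on a signal of effect modification at the end of section 4 concerns the pre-specified subgroups, and the list in section 3.10.3 has no thirst group.
- Whether a graded pattern is false depends on assuming hidden thirst below 8. Appendix 2 treats 8 as the absence of thirst. On that reading, a smaller effect in the lowest group is real on the scale analysed.

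All three stand. It is also fair that, with baseline grouping, the comparison of arms within the lowest group remains randomised and its constant covariate does no harm. Scores there can rise: 22% to 53% of simulated control patients in that group were above 8 at month 3. KCCQ and EQ-5D-5L by thirst group are untouched.

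On week-6 intake, one can say that nobody would take such a p-value seriously and that the comparison is meant descriptively. The text does not say so: it carries over the whole endpoint list together with the section 3.11 test.

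What remains is that the SAP does not separate attenuation at the scale limit from a true difference in thirst relief, and that one of its specified tests is circular.

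**Conclusion.** The concern holds in a limited form.

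The week-6 intake comparison between the below-2 L and above-2 L groups is circular as written. That follows from the text alone; only its illustrated size (about 640 ml) rests on assumed inputs.

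For TDS-HF by thirst group, if grouping is at baseline, the effect in the score-8 group is attenuated, and differences between groups cannot be taken as evidence of effect modification of thirst relief. The sizes (about -0.4 to -0.7 in the lowest group against -2.1 in the highest, at a 1.5-point overall difference) rest on the latent-normal model, a uniform effect and correlations of 0.72 to 0.88.

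A reader might also infer a threat to the trial's main conclusions. There is none: under section 3.3 only the primary and key secondary endpoints are tested hierarchically, and neither depends on these supportive sub-analyses.

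**What to change.** In SAP section 4:
- **Fluid-management analyses 2 and 3:** remove week-6 fluid intake from the endpoints tested, and show it descriptively by group.
- **Thirst aim 2:** state that the groups use baseline TDS-HF. Draw the conclusion on thirst status from the KCCQ scores and EQ-5D-5L. Show TDS-HF by thirst group descriptively, noting that the lowest group is at the scale minimum; alternatively, leave the score-8 group out of any TDS-HF contrast.

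The cost is a few sentences and one exploratory TDS-HF contrast fewer. No further data are needed, and the sample size and the main analyses do not change.

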Appendix 1: Proposed tables and figures

All tables and figures are drafts and will not necessarily be included in the final papers in this form.

1. Study disposition figure

2. Baseline characteristics table

	Total (N = ***)	Fluid restriction (N = ***)	Liberal fluid intake (N = ***)
Age, years			
Male			
White†			
Quality of life			
KCCQ-OSS			
TDS-HF			
EQ-5D-5L			
NYHA functional class			
II			
III			
LVEF			
%			
HFrEF			
HFmrEF			
HFpEF			
Pathogenesis HF			
Ischemic			
Dilating			
Hypertension			
Valvular			
Drug-induced Other			
Unknown			
HF duration, years			
Fluid management Fluid restriction of 1L			
Fluid restriction of 1.5L			
Fluid restriction of 1.5 to 2L			
Fluid restriction of 1.5 to 2.			
Liberal fluid intake			
Other			
HF treatment			
ACEi or ARB			
ARNI			
β-blocker			
Digoxin			
MRA			
SGLT2i			
Loop diuretics			
Thiazides			
GDMT score‡			
ICD			
CRT			

Medical history

Atrial fibrillation or flutter

BMI, kg/m²

COPD

DM

Hypertension

Currently smoking

Laboratory results

Haemoglobin, mmol/l

Sodium, mmol/l

Potassium, mmol/l

Urea, mmol/l

eGFR, ml/min/1.73m²

Nt-proBNP, pg/ml

Osmolality, mosm/kg

3. Outcomes

Table: 'Primary and secondary outcomes.'

	Fluid restriction (N = ***)	Liberal fluid intake (N = ***)	P value
Primary outcome			
KCCQ-OSS			
Key secondary outcome			
TDS-HF			
Other secondary outcome			
KCCQ-CSS			
KCCQ-TSS			
KCCQ-PLS			
KCCQ-QoL			
KCCQ-SBS			
KCCQ-SES			
KCCQ-SFS			
KCCQ-SLS			
KCCQ-SSS			
KCCQ-OSS (-5 to +5)			
KCCQ-OSS (-5 or less)			
KCCQ-OSS (+5 or more)			
EQ-5D-5L			
Reported fluid intake			
Safety			
Death			
All-cause hospitalisation			
IV-loop diuretics usage			
Composite of the above			
Acute kidney injury†			
Values are mean ± SD or median (int	erquartile range)		

alues are mean ± SD or median (interquartile range)

EQ-5D-5L = European Quality of Life Five Dimensions Five Levels questionnaire; KCCQ = Kansas City Cardiomyopathy Questionnaire; -CSS = Clinical Summary Score; -TSS = Total Symptom Score; -OSS = Overall Summary Score; -PLS = Physical Limitation Score; -QoL = Quality of Life; -SBS = Symptom Burden Score; -SES = Self-Efficacy Score; -SFS = Symptom Frequency Score; -SLS = Social Limitation Score; -SSS = Symptom Stability Score; IV = intravenous; TDS-HF = Thirst Distress Scale for patients with HF;

[†] Acute kidney injury is defined as a 50% decline in estimated glomerular filtration rate relative to baseline, or decrease of >30 ml/min/1.73 m^2 and to a value below 60 ml/min/1.73 m^2 .

Figure: primary outcome: 'Mean KCCQ-OSS score at baseline and month 3 visit.'

For illustration purposes only. Hypothetical data.

[figure not shown]
[figure not shown]
[figure not shown]

Figure secondary outcome: 'Mean quality of life questionnaires scores at month 3 visit.' For illustration purposes only. Hypothetical data.

Figure secondary outcome: 'KCCQ-OSS at month 3 improvement and deterioration compared to baseline.' For illustration purposes only. Hypothetical data.

